- g. Exercise-related adverse events will be collected from baseline/screening through the End of Study visit for all subjects. All other adverse events will be collected from the start of study drug. Serious adverse events are recorded from the time the informed consent form is signed until the Safety Follow-Up visit (or screen failure). In the event of no Safety Follow-Up visit, adverse event information will be collected through 30 days after the last dose of study drug. Subjects should be contacted by phone for adverse event follow-up if they do not come to the clinic for the Safety Follow-Up visit.
- h. Clinical laboratory tests may be performed at unscheduled visits if clinically indicated.
- i. Labs performed as part of screening are good for 30 days before randomization and do not need to be repeated.
- j. PSA may be performed at Unscheduled Visits as indicated to confirm PSA progression. No subject should discontinue study drug due to PSA rise during the first 12 weeks of therapy. Subjects with PSA progression on or after Week 17 must have progression confirmed by a second consecutive assessment conducted at least 3 weeks later before study drug discontinuation.
- k. CT of the abdomen and pelvis and bone scans should be performed to document that there is no definite evidence of metastatic disease at the time of screening. MRI of the abdomen and pelvis may be used in place of the CT.
- l. Baseline imaging performed per NCCN Guidelines⁸⁶ prior to informed consent as standard of care may be used so long as it is performed within 84 days prior to randomization.
- m. ADT (GnRH analogue) will be administered as per standard of care to maintain a castrate level of serum testosterone (<50 ng/dL) from Day 29 to Day 252.
- n. Muscular Strength and Muscular Endurance must be done at least 24 hours before or after CPET to allow adequate recovery time.
- o. Both the usual care group and the exercise training group will have a 4 week lead-in before starting ADT plus enzalutamide; only the exercise training group will undergo exercise training during this time.
- p. Day 1 is defined as the randomization day for Arm A (non-exercise) and the start of exercise for Arm B.
- q. Randomization may be done on Day 1 prior to the patient's exercise training session(s) for that week.
- r. DEXA scan for body composition should be fasting, if possible.

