9.5 Lead-In Period

Subjects will be randomized to usual care or exercise training up to 14 days prior to Day 1, but only after eligibility is confirmed and baseline exercise testing (specifically, CPET) has been performed. See **Sections 6.1.4** and **9.4** for randomization details. See also **Schedule of Events**, above.

Arm A, ENZ – ADT plus Usual Care: Subjects randomized to usual care will be asked not to make any changes in their physical activity beginning on Day 1. These subjects will start ENZ – ADT on Day 29 (week 5) after the 4 week lead-in period. This delay is felt to be insignificant from a clinical perspective. While two Phase III studies are currently examining this question (NCT00439751; NCT00110162), the delay in initiation of ADT in these studies is much longer than 4 weeks. There is currently no evidence that a delay, especially one as short as 4 weeks, in starting ADT in men with non-metastatic prostate cancer, affects outcomes.⁸⁸

Arm B, ENZ – ADT plus Exercise Training: Subjects randomized to exercise training will begin the exercise training program detailed below beginning on Day 1. The goal for the ENZ-ADT plus exercise training will be 3 supervised exercise sessions per week at an intensity between 50 and 100% of the individually determined exercise capacity (at baseline) for aerobic training and an intensity between 60% and 80% of one-repetition maximum (1-RM) for resistance training for 30-90 minutes/session. The exercise training intervention is designed such that participants begin exercising at a low intensity (~50%-60% VO₂peak) that is subsequently increased to more moderate to vigorous intensity (~70%-80% VO₂peak) when appropriate. All interventions will be individually tailored to each subject following the principles of aerobic or resistance training prescription guidelines for adults as recommended by the American College of Sports Medicine (ACSM).⁸⁹ All exercise sessions will also be performed in a supervised setting with one-on-one supervision by certified exercise physiologists, physical therapists, exercise physiology students under the supervision of an ACSM-certified exercise physiologist, or trained designee. The exercise prescription for each subject will be created centrally by either [name] group at MSKCC or the CPX Lab at Duke based on both the interpretation of the CPET plus Muscular Strength/1-RM data and a standardized template, within 24-48 hours of these tests.

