The major reason for early training during this Lead-In Period is to 'buffer' the expected rapid deleterious impact of hormonal therapy on cardiovascular and skeletal muscle function. This 'pre-treatment' exercise training is hypothesized to attenuate this impact that, in turn, will facilitate higher intensity exercise training during hormonal therapy.

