9.12.3 Correlative Assessments

All Correlative Assessments will be performed at Day 1 and Day 113 (see Schedule of Events at the beginning of this Section for details). Patient reported outcomes will also be performed at Day 252. In addition, a CPET will be performed at Day 29 to assess VO₂peak changes during the Lead-In Period and Metabolomics samples will be drawn at Day 57 to assess for early changes that may predict later changes in metabolic parameters. All samples will be collected in the fasting, pre-exercise state unless otherwise noted below.

Cardiopulmonary Exercise Testing (CPET)

Exercise Capacity will be assessed using a symptom-limited CPET on a motorized treadmill with expired gas analysis to determine VO₂peak, according to guidelines for clinical populations.⁹⁰ All CPET data will be recorded as the highest 30s value elicited during the CPET. During exercise, heart rate and rhythm will be monitored continuously using a 12-lead ECG. Equipment with similar technical specifications will be used across the two study sites to ensure reasonably accurate and precise results.

Physical Functioning / Functional Capacity

Physical Functioning / Functional Capacity will be assessed using the following assessments: chair-stand test, timed up and go, and 6 min walk distance outcomes as described previously.^{91 57,92,93} These measures will complement the exercise capacity measure.

Chair-Stand Test: The 5-repetition chair-stand test measured the time taken to complete 5 repetitions of the sit-to-stand maneuver. All sit-to-stand maneuvers will be performed from a chair without an arm rest at 43cm in height and 47.5cm in depth. Standardized instructions will be provided as follows: "By the count of 3, please stand up and sit down as quickly as possible for

5 times. Place your hands on your lap and do not use them throughout the procedure. Lean your back against the chair's backrest at the end of every repetition." Timing will start when the subject's back left the backrest and will be stopped once the back touched the backrest.

Timed Get Up and Go: Subjects will be required to stand up from a chair with armrests, walk 3m, turn around, return to the chair, and sit down. The time taken to complete this task will be measured in seconds with a stopwatch.⁹³

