12.4.2 Statistical Hypothesis, Model, and Method of Analysis

The primary analysis will be comparison of the change in peak oxygen uptake ($\Delta\text{VO}_2\text{peak}$) from week 1 to week 17 between the usual care and exercise training groups, using a t-test. The primary analysis will be done for complete cases, (i.e. patients with VO_2peak measured at baseline and at week 17) in the ITT population.

Descriptive comparisons of $\Delta\text{VO}_2\text{peak}$ will be done:

- between baseline and end of week 4 to assess the effect of exercise (or usual care) alone,
- between end of week 4 and start of week 17 to assess the effect of exercise during ENZ + ADT treatment, and
- between the start of week 17 and the end of week 36 to assess whether there is a lasting effect of the supervised exercise regimen after it is discontinued.

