12.6 Sample Size Calculation

The primary purpose of this study is to investigate to study the effect of supervised exercise training on cardiopulmonary function in men receiving the combination of enzalutamide (ENZ) and androgen deprivation therapy (ADT) for treatment of hormone-naïve prostate cancer.

The initial sample size calculations was based on the expected change in VO₂peak based on relevant prior reports or unpublished observations by the study team. Regarding the ENZ + ADT group, Segal et al.⁸⁰ reported that VO₂peak showed a mean decrease of 1.4 mL.kg.⁻¹min⁻¹ in 41 men initiating radiation with or without ADT for prostate cancer. During the same period, structured supervised resistance training completely abrogated the decline in VO₂peak observed in the usual care group. In unpublished data from our group among 50 men following prostatectomy for localized prostate cancer, mean VO₂peak was 29.5 mL.kg.⁻¹min⁻¹ (± 5.0 mL.kg.⁻¹min⁻¹). Following baseline assessments, subjects were randomly allocated to supervised aerobic training (n=25) or usual care (n=25) for 6 months. VO₂peak increased by 2.71 ± 3.5 mL.kg⁻¹.min⁻¹ in the exercise group and 0.6 ± 2.2 mL.kg⁻¹.min⁻¹ in the usual care group, resulting in a between group difference of +1.95 mL.kg⁻¹.min⁻¹ that favored the exercise training group (p=0.024).

Against this background, this protocol adopted the following assumptions: (1) a decline of 2.0 mL.kg⁻¹.min⁻¹ ENZ-ADT group from baseline to 16 weeks, and (2) an increase of 1.0 mL.kg⁻¹.min⁻¹ ENZ-ADT plus exercise training group from baseline to 16 weeks, for a between group delta of 3.0 mL.kg⁻¹.min⁻¹, favoring the ENZ-ADT plus exercise training group. A total of 56 subjects (n=28 / per group) provides 80% power to detect a mean 3.0 mL.kg⁻¹.min⁻¹ between group difference in VO₂peak from baseline to post-intervention, assuming a SD of 3.5 mL.kg⁻¹.min⁻¹ and a two-sided alpha of 0.05. These calculations assume a lost-to-follow-up rate of 15%, thus approximately 23 per group will provide evaluable data at 16 weeks post-randomization.

In November 2016, an interim analysis was performed due to the slow accrual and subjective feedback from subjects and exercise physiologists. That is, subjects in the exercise training group (Arm B) seemed to feel and perform better after the 16-week exercise training program compared with the usual care (Arm A) group at

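### The descriptive week 4 to week 17 VO2peak comparison does not isolate exercise given during ENZ + ADT, because only Arm B trained during the lead-in

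*Combined protocol and SAP*

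**What the plan says.** After the primary week 1 to week 17 comparison, Section 12.4.2 lists three descriptive comparisons of VO2peak change, each with a purpose. The first runs from baseline to the end of week 4, for exercise or usual care alone. The second is "between end of week 4 and start of week 17 to assess the effect of exercise during ENZ + ADT treatment". The third covers the period after supervised training ends.

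The lead-in differs by arm. A footnote to the Schedule of Events in Section 9 says that "only the exercise training group will undergo exercise training during this time". Section 9.5 says of Arm A: "Subjects randomized to usual care will be asked not to make any changes in their physical activity beginning on Day 1". The same section gives the reason for training before therapy: this "exercise training is hypothesized to attenuate this impact that, in turn, will facilitate higher intensity exercise training during hormonal therapy".

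Section 9.12.3 gives the week 4 measurement a narrower purpose: "a CPET will be performed at Day 29 to assess VO₂peak changes during the Lead-In Period". The schedule has CPET at baseline, Day 29 and Day 113 only.

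**The concern.** Randomisation makes the arms comparable at baseline. The week 4 value is a post-randomisation outcome that training has already had 4 weeks to change in one arm. A change measured from that point compares men who start ENZ + ADT with different training histories.

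To isolate training given during therapy, one needs men with the same lead-in who then stop. The alternative question, training begun only when therapy begins, needs men who start at week 5. The trial has neither group.

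The stated purpose could therefore mislead in two ways. If lead-in training blunts the hormonal decline, part of the week 4 to 17 difference is carry-over from the lead-in but would be credited to training during therapy. If a lead-in gain is held only because training continues, that benefit is already in the week 4 difference and is subtracted out.

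**Working it through.** **Inputs from Section 12.6.** The initial plan assumes changes of -2.0 (Arm A) and +1.0 (Arm B) mL/kg/min from baseline to 16 weeks, a difference of 3.0, with SD 3.5. The revised plan gives only an effect size of 0.68 SD, with 20 evaluable per arm, one-sided alpha 0.10 and 80% power.

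**The plan's own figures.** The revised power reproduces: 80.1% by noncentral t, 80.8% by normal approximation. So does the initial sample size: 23 per arm gives 81.1% power (22 gives 79.3%), and 23/0.85 = 27.06, rounded up to 28. These concern the primary comparison, which is not in dispute.

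**Definitions (between-arm, B minus A).**
- T = difference in change, week 1 to 17.
- L = difference in change, week 1 to 4.
- X = difference in change, week 4 to 17, so X = T - L.
- C = the week 17 difference from Arm A that lead-in training would leave if training stopped at week 4.
- E = effect of training during ENZ + ADT, given the lead-in: E = T - C = X + (L - C).

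T, L and X can be estimated; C cannot. X equals E only when C = L.

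**Numbers.** The documents give neither L nor C, so both are assumptions. With T = 3.0:

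| Assumed L | X = 3.0 - L | E if the lead-in gain is lost (C = 0) | E if it just persists (C = L) | E if buffering is complete (C = 3.0) |
|---|---|---|---|---|
| 0 | 3.0 | 3.0 | 3.0 | 0 |
| 0.5 | 2.5 | 3.0 | 2.5 | 0 |
| 1.0 | 2.0 | 3.0 | 2.0 | 0 |
| 1.5 | 1.5 | 3.0 | 1.5 | 0 |
| 2.0 | 1.0 | 3.0 | 1.0 | 0 |
| 3.0 | 0 | 3.0 | 0 | 0 |

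Within a row, T, L and X are identical whatever E is, so the data cannot choose between the last three columns.

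**The row L = 1.0.** Suppose Arm A goes 0, 0, -2.0 and Arm B goes 0, +1.0, +1.0 at baseline, week 4 and week 17. Then X = 2.0.
- Without buffering, C lies between 0 and 1.0, so E lies between 2.0 and 3.0 and X is correct or too small.
- With half of Arm A's decline prevented by the lead-in and the gain kept, C = 1.0 + 1.0 = 2.0. Then E = 3.0 - 2.0 = 1.0 and X is too large.
- With the whole decline prevented and the gain kept, C = 1.0 + 2.0 = 3.0 and E = 0.

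**Revised effect size.** If the SD is still 3.5 (an assumption), T = 0.68 x 3.5 = 2.38. With L = 1.0, X = 1.38, and E without buffering is 1.38 to 2.38.

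**Precision.** With 20 per arm and a change SD of 3.5 assumed for this window, the standard error of X is 3.5 x sqrt(2/20) = 1.11. Sampling error comes on top of the identification problem.

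**The case against.** The strongest reply is that little depends on this line. It is descriptive, with no test, alpha or decision attached. Section 5 names the key comparisons as Day 1 to Day 113 and Day 1 to Day 252. Arm B's intervention is defined as a 16-week programme that includes the lead-in, and the randomised week 1 to 17 comparison evaluates it. All of that stands. It limits the consequence, but it does not correct the purpose that the bullet states.

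The bullet also does not say that the comparison is between arms. Section 12.4.1 speaks of change in each group, and the first bullet mentions usual care. Between-arm is the natural reading of a comparison of exercise, but it is an inference. A within-arm reading would not rescue the label, because it would mix the exercise effect with the drug effect.

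Three stronger readings are tempting and are not supported:
- **That the result fits anything from no effect to the full planned effect.** The zero end needs complete buffering, or a lead-in difference equal to the whole 3.0. Section 9.5 says only that the impact is attenuated, and part of the benefit it describes runs through harder training during therapy. A difference of 3.0 in 4 weeks would exceed the 2.71 increase that Section 12.6 reports after 6 months of aerobic training.
- **That this is the figure the trial will be judged on.** Nothing in the documents says so.
- **That the first two windows are strongly negatively correlated because they share the Day 29 test.** The size depends on an assumed covariance. Section 12.6's SD of 5.0 and change SD of 3.5 imply a within-patient correlation of 1 - 3.5²/(2 x 5.0²) = 0.755. Compound symmetry then gives about -0.5 between the two windows. An AR(1) structure with 0.755 between adjacent visits gives -(1 - 0.755)/2, about -0.12.

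**Conclusion.** The point holds as a matter of interpretation. Read between arms, the week 4 to 17 comparison is the total difference minus the week 4 difference. It equals the effect of training during ENZ + ADT only if the lead-in difference would have persisted unchanged without further training. No arm stops training at week 4 and no CPET follows Day 113, so the trial cannot check this.

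In the illustration (total 3.0 from the initial plan, assumed week 4 difference 1.0), a reading of 2.0 understates the effect by up to 1.0 without buffering. It overstates the effect if buffering is strong enough that the lead-in alone would leave more than 1.0 at week 17. That the label is unsupported follows from the design; the sizes rest on the assumed values.

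A reader might infer that the primary result or the sample size is undermined. Neither is: the week 1 to 17 comparison starts from a measurement taken before randomisation.

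**What to change.** In Section 12.4.2:
- Treat as interpretable the two between-arm comparisons anchored at baseline, both already planned: baseline to Day 29 (effect of lead-in exercise) and baseline to Day 113 (effect of the whole 16-week programme). Say explicitly that they are between arms.
- Relabel the week 4 to 17 bullet: *change in the between-arm difference after ENZ + ADT start, in men with versus without lead-in training*.
- Add one sentence: this comparison does not separate exercise during ENZ + ADT from carry-over of the lead-in.

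This costs wording and one table label. It needs no new data, visits or patients, and the primary analysis is unchanged. The small downside is giving up a separate descriptive claim about exercise during ENZ + ADT.

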12.4.3 Handling of missing values, censoring, and discontinuations

The primary analysis from baseline to week 17 will include only complete cases.

Patients without VO_2peak measured at week 17 who have one or more measurements during the period from week 17 to the end of week 36 will have their week 17 measurement estimated by interpolation from the end of week 4 to the closest measurement following week 17. A sensitivity analysis will be done including these patients with complete cases.

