9.6 Treatment Period 1: ENZ-ADT plus either Usual Care or Exercise Training

Arm A, ENZ – ADT plus Usual Care: Beginning on Day 29 (week 5), subjects will be treated with androgen deprivation therapy (ADT) per standard of care (orchiectomy, GnRH agonist, or GnRH antagonist to maintain total testosterone <50 ng/dl for the remaining 32 weeks of the study). In addition, subjects will take enzalutamide (ENZ) 160 mg by mouth daily for the remaining 32 weeks of the study. The dosing of both the GnRH agonist and enzalutamide (160 mg daily) is the standard-of-care dosing. The treatment duration of approximately 8 months was selected to achieve maximal efficacy while minimizing toxicity and is based on intermittent hormonal therapy regimens studied in Phase III clinical trials.^{22,23} Concomitant medication will be evaluated at every clinic visit during enzalutamide therapy. Concomitant medications include all vitamins, herbal remedies, over the counter, and prescription medications.

Arm B, ENZ – ADT plus Exercise Training: Beginning on Day 29 (week 5), Subjects randomly allocated to this group will receive the same ADT-ENZ regimen as described above. In addition, subjects will continue the defined exercise training initiated during the Lead-In Period for a total of 16 weeks (through Day 113, week 17).

The window is ± 7 days for this period, EXCEPT Day 29 (week 5) which has a window of ± 3 days. See **Schedule of Events**, above.

Subject data to be collected during Treatment Period 1 includes:

- Physical Exam
- Height, Weight, BMI
- Vital Signs
- Performance Status (ECOG)
- Concomitant Medications
- Adverse Events
- CBC with Platelets (hemoglobin, hematocrit, platelet count, white blood cell count, total [absolute] neutrophils)
- Serum Chemistry (sodium, potassium, chloride, total CO₂ [bicarbonate], calcium, BUN, creatinine, glucose, albumin, total bilirubin, total protein, alkaline phosphatase, AST, ALT)
- Testosterone (Day 57 and 113)
- PSA
- CPET (Day 29 and Day 113)
- Chair Stand (Day 113)
- Timed Up and Go (Day 113)
- 6 Minute Walk Distance (Day 113; **Duke patients only**)
- Muscular Strength (*at least 24 hours before or after CPET on Week 4, Week 10 (not in conjunction with CPET) and week 17 in treatment period 2*)
- Muscle CSA (MRI; Day 113; **protocol v1-v15 only**)
- Muscular Endurance (*must be at least 24 hours before or after CPET to allow for adequate recovery on week 4, week 10 (not in conjunction with CPET) and week 17 in treatment period 2*)

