12.1 Analysis Sets

The intent-to-treat (ITT) population will consist of all randomized patients. The modified intent-to-treat (ITT) population will consist of all randomized patients who have both a baseline and week 17 evaluation. In the ITT analyses and the modified ITT analyses patients will be analyzed according to the study arm to which they were randomized. The modified ITT population will be the primary analysis population.

The per-protocol population will consist of all randomized patients with both baseline and week 17 measurements for the primary endpoint and prior to any analysis: have been deemed compliant and properly evaluated for efficacy per investigator, satisfied all inclusion and exclusion criteria, and correctly assigned treatment.

The safety population will be all patients with at least one safety evaluation.

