the same time point. A difference in the point estimates of $\Delta\text{VO}_2\text{peak}$ (week 1 to week 17) between groups was seen in the first 8 subjects who had completed testing for the primary endpoint of $\Delta\text{VO}_2\text{peak}$ at week 17 (N=4 each in the usual care and exercise training groups), suggesting less decline of VO_2peak in Arm B. Based on the interim analysis data, the study statisticians revised the sample size calculation.

We expect to use a one-sided t-test to check whether Arm B has a significant increase in VO_2peak from the baseline compared to Arm A. When each group has 20 evaluable subjects for significance level 0.10, we have 80% power to reject the null hypothesis that the two groups have the same change of VO_2peak given the effect size is 0.68 (the ratio of mean difference over common standard deviation). In case the test result is not significant, we will report the mean reduction descriptively with 95% confidence interval for this pilot study.

In summary, the revised sample size estimate is 40 total evaluable subjects, or 20 subjects in each arm.

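### The complete-case primary t-test ignores the Day 29 CPET of men lost before week 17, so loss that depends on early response and differs by arm can bias the exercise effect in either direction

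*Combined protocol and SAP*

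**What the plan says.** Section 12.4.2 makes the primary test a t-test on the change in VO2peak from week 1 to week 17: "The primary analysis will be done for complete cases". Section 12.4.3 repeats the restriction: "The primary analysis from baseline to week 17 will include only complete cases". Section 12.1 defines the modified ITT set by having both a baseline and a week 17 evaluation, and adds: "The modified ITT population will be the primary analysis population". Section 6.4, by contrast, counts any man with a baseline measurement as evaluable for the primary analysis.

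The Day 29 test is scheduled in both arms. Section 9.6 lists "CPET (Day 29 and Day 113" among the Treatment Period 1 data, and Section 9.12.3 says "a CPET will be performed at Day 29 to assess" VO2peak change over the lead-in. The Schedule of Events shows no CPET after Day 113.

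Two sensitivity analyses bear on missing week 17 values. Section 12.4.3 interpolates between the end of week 4 and a measurement after week 17. Section 12.5 repeats the primary analysis with LOCF. Section 12.5 also names a repeated-measures model, but for secondary and exploratory measures.

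On loss, the superseded calculation in Section 12.6 says "These calculations assume a lost-to-follow-up rate of 15" per cent. The revised calculation gives no loss rate. It needs 40 evaluable men, and Section 6.1 enrols 40.

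**The concern.** The complete-case t-test compares the men who stayed. If those who leave are mainly the ones doing badly at Day 29, the stayers' mean change is too favourable. When this happens to a different degree in the two arms, the shift does not cancel in the arm difference.

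Different loss is plausible. The trial is open label, only Arm B attends three supervised sessions a week, and the investigator may withdraw men for adverse events or abnormal results (9.11.1). The lead-in is also meant to produce an arm difference by Day 29 (9.5), so even one common rule for leaving could act unequally.

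At stake are the primary estimate and the one-sided 0.10 error rate, in a design with no allowance for loss. The measurement that would relax the assumption is already collected.

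**Working it through.** **1. The plan's own figure.** Section 12.6: "We expect to use a one-sided t-test", level 0.10, effect size 0.68, 20 evaluable per arm. Noncentrality = 0.68 x sqrt(20/2) = 2.150 on 38 df. Power is 0.801, so the stated 80% is reproduced.

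**2. Inputs.** From Section 12.6: baseline SD 5.0 and change SD 3.5. The 3.5 belongs to the superseded calculation and is used only to express results in mL/kg/min: 0.68 x 3.5 = 2.38. The implied baseline-to-week-17 correlation is 1 - 3.5²/(2 x 25) = 0.755.

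Assumed, not in the documents: correlation r of 0.80 to 0.85 between Day 29 and each other visit; logistic loss on Day 29 change (slope 0.3 or 0.6 per mL/kg/min); and the loss rate in each arm. The correlation between Day 29 change and week 17 change is then 25 x (1 - 0.755) / [sqrt(50(1 - r)) x 3.5]. This is 6.125/(3.162 x 3.5) = 0.55 at r = 0.80 and 6.125/(2.739 x 3.5) = 0.64 at r = 0.85.

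**3. Bias of the complete-case t-test** (simulation, 20 per arm, nominal rate 10%):

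| Loss, Arm A v Arm B | Bias, mL/kg/min | False-positive rate |
|---|---|---|
| 5% v 20% | about +0.2 to +0.4 | about 14-17% |
| 5% v 10% | about +0.1 | about 12% |
| 15% v 15%, equal dependence | about 0 | about 10% |
| 20% v 5% | about -0.25 | about 7% |

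The range in the first row spans both slopes. The last row is for the milder slope, so the table does not show that bias against exercise is the smaller risk. A complete-case ANCOVA on baseline keeps about 75-90% of the bias, because the information on who leaves lies in the Day 29 value. The longitudinal likelihood estimator stayed within 0.06 of the truth, with false-positive rates of 9-11%.

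**4. Second parameterisation.** Take 15% loss, related to Day 29 change in one arm only (log-odds slope 1 per SD), with correlation rho between the two changes. The bias is rho x 3.5 x (shift of the stayers' mean Day 29 change, in SDs). At rho = 0.5 the simulated bias was +0.233, so the shift is 0.233/(0.5 x 3.5) = 0.133 SD. The formula then gives 0.14 at rho = 0.3 and 0.33 at rho = 0.7, in line with the simulated +0.13 and +0.33. The false-positive rate is 12-15%. Placing the dependence in usual care gives -0.14 to -0.33. One rule on absolute Day 29 change in both arms, with arms already 1.19 to 2.38 apart at Day 29, gives -0.04 to -0.15 (slope 1) or -0.07 to -0.33 (slope 2). With no Day 29 difference it gives about 0.

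**5. Power at balanced 15% loss.** With 17 completers per arm, noncentrality = 0.68 x sqrt(17/2) = 1.983 and power is 0.750. Using Day 29 data, the variance of an arm mean is SD² x [(1 - rho²)/17 + rho²/20]. At rho = 0.5 this is SD² x (0.04412 + 0.0125) = SD²/17.66, and power is 0.762. At rho = 0.7 power is 0.774. The gain is 1.2 to 2.4 points. In the simulations, power was 74-76% for the t-test, 76-79% for complete-case ANCOVA and 77-79% for the longitudinal model. One pair of runs separates the parts:

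| r | t-test | ANCOVA | Longitudinal | From baseline | From Day 29 |
|---|---|---|---|---|---|
| 0.80 | 76.4% | 78.6% | 79.4% | 2.2 | 0.8 |
| 0.85 | 74.7% | 77.2% | 78.9% | 2.5 | 1.7 |

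**6. The existing sensitivity analyses.** Interpolation needs a VO2peak after week 17, and none is scheduled. LOCF substitutes a value from the start of ENZ-ADT for one after 12 weeks of it. If half the effect is present by Day 29 (assumed), purely random 15% loss shifts the LOCF estimate by about 0.15 x (2.38 - 1.19) = 0.18 against exercise (simulated: about -0.17).

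**The case against.** The strongest reply is that nothing in the documents shows unequal or response-related loss. The only loss figure is 15% overall, from a superseded calculation. Three sessions a week is a reason to stop training, not necessarily to miss the Day 113 CPET, and a man who stops training but attends is analysed as randomised (12.1). Lost men are to be pursued (9.10), and reasons for loss are tabulated by arm (12.3), so an imbalance would be visible. This stands as a limit on confidence. It does not make the complete-case estimate safe, because a table of reasons does not correct it.

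A reader might infer that the plan favours exercise. The documents do not support a sign: disappointed usual-care men in an open-label trial could leave just as readily, and the bias then reverses. Rates of 19-24% can be produced, but they take 30% loss in Arm B and steep dependence, for which the documents give no basis.

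A reader might also infer that the t-test is valid only if loss is unrelated to response. That is too strong, since equal loss with equal dependence roughly cancels.

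Nor are Day 29 values missing from the whole plan. The LOCF analysis uses them, though only as a sensitivity analysis that does not repair the primary estimate.

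**Conclusion.** The point holds as a conditional weakness of the primary estimator. If loss depends on early response and differs by arm in amount or pattern, the exercise effect is biased in either direction. For one-arm excess loss of the size examined (20% v 5%), the bias is about 0.2 to 0.4 mL/kg/min, or 8% to 17% of the 2.38 that the trial is powered for (0.2/2.38 and 0.4/2.38). The one-sided error rate moves to about 14-17% when Arm B loses more and about 7% when Arm A does. At 5% v 10% loss the effect is small. These sizes rest on assumed loss rates, mechanism and correlations.

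It is tempting to add that Day 29 data would restore the power lost to dropout. They would not: about 1-2 points are recoverable, and most of the longitudinal model's advantage over the t-test comes from adjusting for baseline. The case for change rests on protection against bias, at low cost.

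**What to change.** In Sections 12.4.2 and 12.4.3, make the primary analysis a likelihood-based repeated-measures model in all randomised men with a baseline CPET, which also agrees with Section 6.4:

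- outcomes: VO2peak at baseline, Day 29 and Day 113;
- terms: visit and arm-by-visit, with a common baseline mean;
- unstructured covariance and small-sample degrees of freedom;
- primary contrast: arm difference in change from baseline to Day 113, at the stated one-sided 0.10 level.

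Align the primary population in Section 12.1, and keep the complete-case t-test as supportive. Because Section 12.6 records a by-arm look at the first 8 men, date the change before any further by-arm data are seen.

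The cost is SAP wording and slightly more analysis, with no new data. The model assumes that loss is explained by observed baseline and Day 29 values, and men lost before Day 29 contribute only their baseline.
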